108 inflammatory medication) will be provided for those patients randomized to the experimental  
109 group, once daily for fourteen days following the manipulation under anesthesia. Aspirin, used  
110 routinely for DVT prophylaxis post-operatively, did not restrict patients from participation in this  
111 study. Patients who are on NSAIDs prior to MUA, is ok to enroll. Patient demographics were  
112 noted, including age at index arthroplasty, sex, body mass index (BMI), ASA score, and  
113 Charlson Index.

114

115 ***Randomization***

116 Patients will be randomized into one of 2 groups: (1) MUA only (i.e. control group) or (2) MUA  
117 plus 8 mg of IV dexamethasone immediately before MUA, followed by 2 weeks of PO celecoxib  
118 (200 mg daily) (experimental group). Assignment of patients into either group will be made prior  
119 to the initiation of enrollment for the study. Patients will be randomized using a computer  
120 generated (SAS PROC) block randomization schedule to ensure equivalent numbers of patients  
121 in each group over the course of the study in case early stopping is required. The randomization  
122 schedule will be generated by the Mayo Clinic Department of Epidemiology and Biostatistics  
123 with the randomization list provided to the investigators prior to initiation of patient recruitment.  
124 Neither the patient nor the treating physician were blinded the randomization group.

125

126 ***Manipulation Under Anesthesia***

127 Patients will undergo MUA per their institutional protocol. As previously noted, these will be  
128 completed between 4 and 10 weeks postoperatively for flexion < 90 degrees. Patients will  
129 receive sedation per their institutional protocol. Physical therapy (either supervised or  
130 unsupervised) will be prescribed 2 -3 times per week for 4 – 6 weeks thereafter.

131

132 ***Outcome Measures***

133 The primary outcome measure will be knee range of motion, including both passive and active  
134 flexion and extension 6 weeks after the manipulation and 1 year from the date of the TKA.  
135 Secondary outcomes will include comparison of Knee Society Scores (KSS), 12-item Short  
136 Form Survey (SF-12v2), Knee Injury and Osteoarthritis Outcome Score (KOOS), and the  
137 Promise-29 outcome form (Appendices 1-4). Outcomes will be documented pre-MUA, 6 weeks

138 after the MUA, and 1 year after the TKA. A standardize evaluation form will be shared amongst  

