139 all participating sites, and will be used consistently for all patients (Appendix 1-4).

140

141 ***Power Analysis***

142 The mean and standard deviation for sample size calculation were derived from a study by  
143 Yercan et al. In that study, the authors found that the mean ROM following MUA was  $114^\circ \pm$   
144  $16^\circ$ . We hypothesized that a  $10^\circ$  difference in total range of motion would constitute a  
145 clinically significant difference. With a type I error rate of 5%, 108 total patients (54 per arm) are  
146 required to have 90% power to detect this difference. Accounting for a dropout rate of 20%, 65  
147 patients per arm (130 total patients) will be recruited.

148

149 ***Statistical Analysis***

150 All data will be summarized and reported descriptively using appropriate summary statistics,  
151 including mean and standard deviation (SD) for continuous variables, and count and percentage  
152 for categorical variables. The analysis was focused on the two primary study outcomes: range of  
153 motion (total arc of motion as well as angle of terminal knee flexion, measured in degrees), and  
154 subjective outcome (KSS, SF-12v2, KOOS, and PROMIS). Outcomes were compared between  
155 the two study groups using two-sample t-tests if the data are approximately normally distributed;  
156 if the data are not sufficiently normally distributed, non-parametric Wilcoxon rank sum tests was  
157 used. Since the subjects were assigned to the study groups in a randomized manner, no  
158 significant differences between the subjects in the two groups were expected. However,  
159 apparent differences in subject demographics or baseline clinical data were evaluated, and  
160 further analysis was undertaken using multivariable modeling to compare the two groups while

161 adjusting for other important variables. When necessary and appropriate, the analysis was  
162 adjusted for enrolling center. Categorical outcomes were analyzed using chi-square tests and  
163 logistic regression. Separate analyses were performed for the 6-week and 1-year outcomes. All  
164 statistical tests were two-sided and p-values less than 0.05 will be considered significant.

165

166 ***Sources of Funding***

167 This study is partially supported by the Knee Society Branded Multi-Center Randomized Clinical  
168 Trial Grant.

169  
170  
171  
172  
173  
174  
175  
176  
177  
178  
179  
180  
181  
182  
183  
184  
185  
186  

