**Table 1. List of participating institutions included**

Aria 3B Orthopaedic Specialists  
Colorado Joint Replacement  
Duke University Medical Center  
HipKnee Arkansas Foundation  
Hospital for Joint Diseases  
Hospital for Special Surgery  
Houston Methodist  
Joint Implant Surgeons  
Mayo Clinic  
New York-Presbyterian at Columbia University  
OrthoCarolina  
Rothman Institute  
Rush University Medical Center  
  
Cleveland Clinic  
University of Nebraska Medical Center  
University of Utah Orthopaedic Center

214  
215  
216  
217  
218  
219  
220  
221  
222  
223  
224  
225  
226

227  
228  
229  
230  
231  
232  
233  
234  
235  
236  
237  
238

239 **Table 2.** Baseline demographics and clinical characteristics

Demographic and Clinical Characteristics	MUA (N = X)	MUA + AI (N = X)
Demographic Characteristics		
Age (year)		
Sex (female/male) (no. of patients)		
Weight (kg)		
Height (cm)		
BMI (kg/m  )		
ASA Status (no. of patients)		
Implant Type		
Range of Motion		
Total		
Flexion Contracture		
Extension Deficit		

240  
241  
242  
243  
244  
245  
246  
247  
248  
249  
250  
251

252

253

254

255

256

257 **Table 3.** Outcome following manipulation under anesthesia for stiffness after total knee  
 258 arthroplasty

Blood Loss, Drain Output, and Rate of Blood Transfusions	MUA (N = X)	MUA + AI (N = X)	p value
Six Week ROM Total Pre-Manipulation Flexion Total 6 weeks Post-MUA Flexion < 90 degrees < 80 degrees Total 6 weeks Post-MUA Flexion < 90 degrees < 80 degrees			
Six Week Subjective Outcome KSS SF-12v2 KOOS Promis 29			

Blood Loss, Drain Output, and Rate of Blood Transfusions	MUA (N = X)	MUA + AI (N = X)	p value
One Year ROM Total Pre-Manipulation Flexion Total 6 weeks Post-MUA Flexion < 90 degrees < 80 degrees Total 6 weeks Post-MUA Flexion < 90 degrees < 80 degrees			
One Year Subjective Outcome KSS SF-12v2 KOOS Promis 29			

259

260

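### The planned range-of-motion comparison ignores the recorded pre-MUA value, and the plan does not say whether the unadjusted or the adjusted result decides; one pre-specified ANCOVA would settle both

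*Combined protocol and SAP*

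**What the plan says.** - **First comparison (Statistical Analysis).** Outcomes are compared between "the two study groups using two-sample t-tests if the data are approximately normally distributed", and otherwise by Wilcoxon rank sum test. Neither uses a covariate.
- **Further modelling (same section).** The text then says that "apparent differences in subject demographics or baseline clinical data were evaluated, and" "further analysis was undertaken using multivariable modeling to compare the two groups while" "adjusting for other important variables. When necessary and appropriate, the analysis was" adjusted for enrolling centre. No covariate is named, no rule says when centre enters, and the modelling is not ranked against the first comparison.
- **Baseline data.** Outcome Measures names ROM as primary and schedules outcomes before the manipulation: "Promise-29 outcome form (Appendices 1-4). Outcomes will be documented pre-MUA, 6 weeks" after it, and 1 year after the TKA. Table 2, "Baseline demographics and clinical characteristics", has a row for total ROM. The Table 3 shell lists the pre-manipulation value beside the follow-up values ("Six Week ROM Total Pre-Manipulation Flexion Total 6 weeks Post-MUA Flexion"). The analysis text never puts that value into a model.
- **Sample size (Power Analysis).** The target is a 10-degree difference in total ROM with SD 16: "clinically significant difference. With a type I error rate of 5%, 108 total patients (54 per arm) are" needed for 90% power. The raw SD is used, so the calculation matches an unadjusted comparison.
- **Reporting.** Table 3 has a p-value column and no interval. The Statistical Analysis section does not mention one either.

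**The concern.** There are two separate weaknesses.

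**Precision.** Pre-MUA ROM is the baseline value of the primary outcome and will be on file for every patient measured. Leaving it out forgoes whatever variance it explains. The gain may be small, but it costs almost nothing to take.

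**Priority.** The natural reading is that the unadjusted test is the main comparison and the modelling is supportive, but the plan does not say so. Covariates, the prompt for adjusting and the centre rule would all be settled after data are available, in a trial where neither patient nor physician is blinded. If the unadjusted and adjusted p-values fall on opposite sides of 0.05, nothing in the plan says which one answers the question.

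No bias and no type I error inflation is claimed for the plan as written.

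**Working it through.** **Inputs from the documents.** Difference 10 degrees; SD 16; two-sided 5%; target power 90%; 54 per arm needed; 65 per arm recruited; 20% dropout; 16 centres.

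**Inputs assumed.** The correlation r between pre-MUA and post-MUA ROM, shown from 0 to 0.5. For the centre question, also centre sizes and the intraclass correlation (ICC).

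**1. The plan's own figure.** n per arm = 2(1.960 + 1.282)² × 16² / 10² = 53.8, so 54 per arm and 108 in total. This reproduces the plan. Power at 54 per arm is 90.1% by the normal approximation and 89.6% by the noncentral t.

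**2. Patients left after dropout.** 65 × 0.80 = 52 per arm.

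**3. Unadjusted t-test, 52 per arm.** SE = 16 × √(2/52) = 3.138, with 102 df. Noncentrality = 10/3.138 = 3.187, so power is 88.4%. The 95% CI half-width is 1.9835 × 3.138 = 6.22 degrees.

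**4. ANCOVA on pre-MUA ROM, n per arm.** SE = 16 × √(1 − r²) × √[(2/n)(1 + 1/(2n − 4))], with 2n − 3 df. The term 1/(2n − 4) is the cost of estimating the slope; at n = 52 it is 1/100, or 1% of variance. Example at r = 0.3: SE = 3.138 × 0.9539 × 1.0050 = 3.008, noncentrality 3.324, power 90.9%, half-width 1.9837 × 3.008 = 5.97.

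| r | Power, 52/arm | CI half-width, 52/arm | Equivalent t-test n per arm | Power, 54/arm |
|---|---|---|---|---|
| t-test | 88.4% | 6.22 | 52 | 89.6% |
| 0 | 88.1% | 6.26 | 51.5 | 89.3% |
| 0.1 | 88.4% | 6.22 | 52.0 | 89.6% |
| 0.2 | 89.4% | 6.13 | 53.6 | 90.5% |
| 0.3 | 90.9% | 5.97 | 56.5 | 91.9% |
| 0.4 | 92.9% | 5.73 | 61.1 | 93.8% |
| 0.5 | 95.2% | 5.42 | 68.3 | 95.9% |

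Break-even is where (1 − r²) × 1.01 is about 1, so r is about 0.10. At 52 per arm, 90% power is reached at r = 0.247. Simulation at 52 per arm (200,000 trials per cell) gave t-test/ANCOVA power of 88.5/88.2% at r = 0, 88.5/89.4% at 0.2 and 88.5/95.2% at 0.5, in line with the formulas.

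**5. How often the two analyses disagree at p < 0.05** (simulated, 52 per arm).

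| r | True difference 10 | True difference 7 |
|---|---|---|
| 0 | 1.3% | 2.5% |
| 0.2 | 3.2% | 6.3% |
| 0.5 | 8.2% | 18.3% |

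The r = 0 row is background disagreement. If either result could be counted as decisive, which the plan does not propose, simulated type I error at 54 per arm would be about 6.5% at r = 0.3 and 7.3% at r = 0.5.

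**6. Centre.** Simulation used 104 patients in 16 uneven centres (assumed sizes from 20 down to 1), unstratified allocation, and a random intercept with Kenward-Roger df on top of ANCOVA. The change in power was about −0.1 points at ICC 0, +0.2 to +0.3 at 0.05 and +0.9 at 0.10. Type I error stayed between 4.95% and 5.24% (simulation SE 0.11 points).

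**7. Non-normality.** With skewed outcomes (skewness −1 and −2), the ANCOVA type I error was 4.85% to 4.99% at 52 per arm. A data-driven switch to Wilcoxon is not needed to protect the error rate in these settings.

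The centre and skewness results each rest on one set of simulations under the stated assumptions.

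**The case against.** **The planned test is legitimate.** An unadjusted t-test in a 1:1 randomized trial is unbiased, and the sample size was built for it. This stands, and it is why the point is an improvement and not an error.

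**The gain may be negligible.** The documents give no correlation, and restricting entry to flexion below 90 degrees may lower it. At r of 0.1 to 0.2 the gain is 0.0 to 0.9 points, and at r = 0.2 the half-width shrinks by less than 0.1 degree. Below about 0.10 adjustment loses slightly. The correlation may also differ between 6 weeks and 1 year. All of this stands, but the worst case is a loss of about 0.3 points against a gain of 6.8 points at r = 0.5 (95.2 − 88.4).

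**The 88.4% has another cause.** Most of the gap below 90% comes from adding 20% to 108 instead of dividing by 0.80, and the rest from the normal approximation. True; it is context only. At 54 per arm the gain from adjustment is much the same.

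**The text already ranks the analyses.** The t-test comes first and the modelling is called further analysis; read literally, the modelling may not even depend on imbalance. One clarifying sentence could name the t-test as decisive. That would settle priority but leave the baseline unused and the covariates and centre rule open.

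**The centre model is elaborate and rests on assumptions.** The text does not mention stratification by centre, so the design as described does not force centre adjustment. Fair; the need is a rule fixed in advance, and the random intercept is one example.

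**Table 3 is an unfinished shell.** It still carries a heading about blood loss, so its columns are weak evidence of what will be reported. Agreed, but the analysis text does not promise an interval either.

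**Conclusion.** The concern holds as a low-cost improvement that should be made. The plan's stated ROM comparison omits a recorded baseline value of the primary outcome, and no sentence says whether the unadjusted or the adjusted result is decisive.

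The precision gain is conditional. At 52 per arm it runs from −0.3 power points at r = 0, through +0.9 at 0.2 (to the rounding of the unrounded powers, 88.43% to 89.35%), to +6.8 at 0.5. It rests on the plan's difference and SD and on an assumed correlation, so confidence in its size is only moderate. The case for naming one decisive analysis does not depend on a high correlation.

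ANCOVA does not settle which time point or which ROM measure is primary. That is a separate multiplicity question.

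**What to change.** - Make the primary comparison an ANCOVA of post-MUA total arc of motion, the variable in the Power Analysis, on treatment and pre-MUA total arc. Use active or passive arc consistently at both times, and say which.
- Fix centre handling in advance. One option is a random intercept for enrolling centre with Kenward-Roger df, reducing to plain ANCOVA if the centre variance is estimated as zero.
- Use this model whatever the observed imbalance or distribution, and state that its result is decisive.
- Report the adjusted mean difference in degrees with its 95% CI, and add that column to Table 3.
- Keep the t-test and Wilcoxon test as sensitivity analyses. Delete the wording that ties modelling to observed baseline differences and leaves centre adjustment to judgement.
- Apply the same baseline adjustment at the other time point and to KSS, SF-12v2, KOOS and PROMIS-29.

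**Cost.** SAP wording and a few lines of code. Every variable is already to be collected, with no added burden on patients or sites. If baseline proves uninformative the loss is about 0.3 power points; if centre does too, about 0.5 in total (simulated 88.4% to 87.9%).

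### ROM at 6 weeks and 1 year is tested visit by visit with 20% dropout expected and no missing-data method, so the 1-year comparison makes no use of the 6-week ROM of patients lost before it

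*Combined protocol and SAP*

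**What the plan says.** Outcome Measures makes ROM the primary outcome at two times, 6 weeks after the manipulation (MUA) and 1 year after the TKA. Readings are also taken before the MUA.

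Power Analysis sizes the trial for a 10-degree "difference in total range of motion would constitute a" clinically significant difference, with SD 16 degrees from a cited study, and states that 108 patients are "required to have 90% power to detect this difference. Accounting for a dropout rate of 20%, 65" per arm being the recruitment target.

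Statistical Analysis compares outcomes between "the two study groups using two-sample t-tests if the data are approximately normally distributed", with a Wilcoxon rank sum test otherwise. It then says: "logistic regression. Separate analyses were performed for the 6-week and 1-year outcomes. All". Multivariable modelling is brought in only after apparent demographic or baseline differences, and center adjustment only when judged necessary. Neither brings the 6-week value into the 1-year comparison.

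The documents contain no analysis population, imputation, repeated-measures model or sensitivity analysis for dropout. Randomization says that neither patient nor treating physician is blinded.

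**The concern.** A t-test or Wilcoxon test on one visit, with no imputation, can use only patients measured at that visit. With a fifth of patients expected to be lost, the 1-year test is then a complete-case comparison. A patient who was measured at 6 weeks and later lost has a reading that helps to predict the missing 1-year value, and the plan leaves it out of that comparison.

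Two things are at stake. If patients with stiffer knees at 6 weeks are more likely to be missing at 1 year, the 1-year treatment difference may be wrong. Some precision that the collected data could supply is also given up.

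**Working it through.** **Inputs from the documents.** Difference 10 degrees, SD 16, two-sided 5%, 90% power, 54 evaluable and 65 recruited per arm, 20% dropout (Power Analysis; sidedness from Statistical Analysis).

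**Assumed, not in the documents.** Correlation ρ between 6-week and 1-year ROM of 0.5, 0.7 or 0.8; SD 16 and a 10-degree effect at both visits; bivariate normal ROM; log-odds of dropout rising by 0.5, 1 or 2 per SD of lower 6-week ROM; about 20% lost overall. For the bias check, all loss falls between the two visits.

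**1. The plan's own figure.** n per arm = 2(1.960 + 1.282)² × 16² / 10² = 53.8, so 54 per arm and 108 in total. This reproduces. The 65 is 54 × 1.2 = 64.8. After 20% loss, 65 × 0.8 = 52 per arm remain, and t-test power is 88.4%.

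**2. Bias of the 1-year complete-case difference.** When dropout depends only on 6-week ROM, the completers' 1-year mean in an arm exceeds that arm's true mean by ρ × S. Here S is the completers' 6-week mean minus the 6-week mean of the whole arm. Hence

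estimated difference = true difference + ρ × (S_exp − S_ctrl).

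S follows by numerical integration of the dropout model. For a true difference of 10 degrees:

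| Log-odds slope | Same rule in both arms: S_ctrl, S_exp (loss ctrl/exp) | Estimate at ρ = 0.5 / 0.7 / 0.8 | Control only: S_ctrl (20% lost per arm, S_exp = 0) | Estimate at ρ = 0.5 / 0.7 / 0.8 |
|---|---|---|---|---|
| 0.5 | 1.72, 1.36 (22%/18%) | 9.82 / 9.75 / 9.71 | 1.54 | 9.23 / 8.92 / 8.77 |
| 1 | 3.32, 2.22 (24%/16%) | 9.45 / 9.23 / 9.12 | 2.77 | 8.61 / 8.06 / 7.78 |
| 2 | 5.35, 2.99 (26%/14%) | 8.82 / 8.35 / 8.11 | 4.19 | 7.91 / 7.07 / 6.65 |

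A likelihood estimate that also uses the 6-week values gave 10.0 in every cell, within simulation error.

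With no true effect and the same rule in both arms, S_exp = S_ctrl and the bias is 0. With no true effect and the control-only rule, the bias runs from −0.5 × 1.54 = −0.8 to −0.8 × 4.19 = −3.4 degrees. The mirror-image rule, stiffness-driven loss in the experimental arm only, gives the same sizes with a plus sign.

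For scale, the standard error of the difference at 52 per arm is 16 × √(2/52) = 3.1 degrees.

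**3. Precision when dropout is non-informative.** With n₆ patients per arm measured at 6 weeks and 52 of them at 1 year,

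effective n = 1 / [(1 − ρ²)/52 + ρ²/n₆].

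- All loss after 6 weeks (n₆ = 65): 54.7 / 57.6 / 59.6, t-test power 90.0% / 91.4% / 92.3% at ρ = 0.5 / 0.7 / 0.8.
- Half of the 13 losses per arm before 6 weeks (n₆ = 58.5): 53.5 / 55.0 / 56.0, power 89.3% / 90.1% / 90.6%.

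**4. Limit of the joint model.** If dropout depends on the unseen 1-year ROM itself (slope 1, control arm only, true difference 10, ρ from 0.5 to 0.9), complete cases give 7.2 and the joint model 7.9 to 9.4. The bias is reduced, not removed.

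**The case against.** Visit-wise tests are a conventional choice in a trial with two follow-up visits, and the documents nowhere say that incomplete patients are excluded. That is fair: complete-case analysis is what the named tests do when nothing else is specified, not something that the plan declares.

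A reader might infer that the 1-year difference is biased whenever dropout follows 6-week ROM. It is not. Under a common rule with no effect, both arm means rise together and the difference is untouched. Under a common rule with a true benefit, the bias is toward the null; at ρ = 0.7 and slope 1 it is 10 − 9.23 = 0.77 degrees, or 0.77/3.1 ≈ 0.25 standard errors. Larger errors, and any spurious difference under no effect, need a dropout pattern that differs by arm. The open-label design makes that possible, but the documents do not show that it will happen.

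A reader might also infer that the 6-week readings of lost patients are thrown away. They still enter the 6-week test, itself a primary comparison, and are unused only at 1 year.

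Nor do the documents say that stiff knees are the ones lost. Patients doing well might equally skip the 1-year visit. The timing of the 20% is not stated either, so the larger power gain is a best case.

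What remains is that the plan expects substantial loss, names a method that ignores relevant data already scheduled for collection, and offers nothing for the missing values.

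**Conclusion.** The point holds in this conditional form. The separate 1-year test is open to bias if dropout depends on 6-week ROM and either treatment has an effect or the dropout pattern differs by arm. Over the assumed range, a true 10 degrees becomes about 9.8 to 8.1 under a common rule and about 9.2 to 6.7 under a control-only rule. The largest shift, 3.35 degrees, is about one standard error. The power gain is modest: from 88.4% to between 89.3% and 92.3%, depending on the correlation and on when patients are lost. All of these figures rest on an assumed correlation and dropout mechanism. This is an inexpensive improvement to the analysis, not a flaw that invalidates the trial.

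**What to change.** Replace the separate ROM tests with one prespecified likelihood-based repeated-measures model of 6-week and 1-year ROM. Include all randomized patients with at least one post-MUA reading, with arm, visit, arm-by-visit interaction and pre-MUA ROM as terms and an unstructured covariance. Fit it for total arc and likewise for terminal flexion, and report the 6-week and 1-year contrasts from it. Both results that the plan wants are kept.

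Add one tipping-point analysis for missing 1-year ROM, because the model corrects only for dropout explained by observed ROM. Patients lost before 6 weeks contribute no outcome to the model, so report their number by arm.

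Fixed terms for all 16 centers and remodelling of every questionnaire are not needed for this purpose. The cost is a rewritten paragraph, a few lines of SAS and a somewhat more complex primary analysis; no extra patients or visits are required.
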